### Additional analysis:

Intention-to-treat-analyses: All participants will be included.

*Per-protocol-analyzes*: All participants with  $\geq 80$  % compliance will be included.

In the intervention group, compliance will be considered as  $\geq 80$  percent of the recommended intake of 200 mg of phytoestrogens, which is equal to  $\geq 160$  mg. In the control group, intakes below 160 mg of phytoestrogens will be considered compliant.

Analysis of hypothesis will be stratified for:

- no use of antibiotics vs. use of antibiotics
- no use of finasteride vs. use of finasteride

Investigate the effects of the intervention diet on plasma concentrations of phytoestrogens: Cohen's Kappa will be used to compare the agreement of classifications in tertiles from estimated intake of phytoestrogens and plasma concentrations of phytoestrogens. (Kappa values <0 will be considered as poor, 0.00-0.20 as slight, 0.21-0.40 as fair, 0.41-0.60 as moderate, 0.61-0.80 as substantial, and 0.81-1.00 as almost perfect). Boxplots will be used to present the data graphically. Linear regressions will be used to investigate the relationships between estimated intake concentrations (explanatory variables) and plasma concentrations of phytoestrogens (outcomes). The regression model will be stratified according to the intervention- and control groups and genotype.

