### HYPOTHESIS

- In men diagnosed with intermediate risk-level prostate cancer, the addition of phytoestrogenrich foods containing 200 mg phytoestrogens per day in six weeks, gives a reduced prostate tumor proliferation compared to an absence of the addition of phytoestrogen-rich foods during the same period.
- 2) If the effect of phytoestrogens on prostate tumor proliferation exists, it is modified by a SNP in the promoter region of the estrogen-beta-gene (rs 2987983-13950).

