### STUDY DESIGN

The study design is shown in Figure 1. Men diagnosed with intermediate-risk prostate cancer T1–T2 (Gleason score <8, PSA <20), scheduled for radical prostatectomy, are identified at the Sahlgrenska University Hospital. Interested men are contacted by phone and a first meeting is scheduled. At the meeting the participants receive verbal and written information and sign an informed consent. A food frequency questionnaire including dietary and living habits and supplements are filled in and baseline blood samples are taken. The men are randomized to a diet or a control group through a closed envelop. All participants receive general dietary advice according to the Swedish National Food Agency (1). Participants are instructed to avoid supplements but no other dietary restrictions are given. The diet group receive a food package including food items high in phytoestrogens. Recipes and serving suggestions for the study diet are also given. The intake of the food items gradually steps up according to a schedule and the items are eaten in specific amounts until the surgery.

The participants are contacted by phone once during the study and a 24-hour recall is performed. The interview is made to control compliance in the study group and to estimate the intake of phytoestrogens in the control group. Near to surgery a similar food frequency questionnaire is filled in and endpoint blood samples are taken. Prostate biopsies are taken at the surgery. Hormones and PSA are analyzed from baseline and endpoint blood samples. The expression of androgen receptor and estrogen receptor alfa and beta are analyzed in tumor material. Tumor proliferation is calculated by ki-67 from prostatectomy specimens at surgery.

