# **Definition of exposure**

The participants in the intervention group are defined as exposed and the participants in the control group are defined as not exposed.

**Group\_intervention** (0=control, 1=intervention)

Intake of different phytoestrogens at endpoint is based on information from the Food Frequency Questionnaire (FFQ) and the 24-h dietary recall.

**Phytoestogens\_EP\_3** (intake of phytoestrogens at endpoint divided in tertiles, calculated from the FFQ)

Lignans\_EP\_3 (intake of lignans at endpoint divided in tertiles, calculated from the FFQ)

Isoflavones\_EP\_3 (intake of isoflavones at endpoint divided in tertiles, calculated from the FFQ)

Coumestrol\_N58\_EP\_2 (dichotomized intake of coumesterol at endpoint, calculated from the FFQ)

Phyto\_24\_recall\_3 (intake of phytoestrogens at the 24-h dietary recall divided in tertiles)

The concentrations of phytoestrogens (daidzein, enterodiol, enterolactone, equol, genistein, glycetein,

Analysis plan: PRODICA, [name]
----------------------------	--------------

lariciresinol, and secoisolariciresinol) in plasma for a sub-group of participants:

**lignans\_EP\_nmol** (plasma levels of lignans at endpoint=enterolactone+ enterodiol+ lariciresinol+ seco\_EP\_nmol)

**lignans\_BL\_nmol** ((plasma levels of lignans at baseline=enterolactone+ enterodiol+ lariciresinol+ seco\_EP\_nmol)

**isoflavones\_EP\_nmol** (plasma levels of isoflavones at endpoint = daidzein\_EP\_nmol + genistein EP nmol + glycitein EP nmol + equol EP nmol)

**isoflavones\_BL\_nmol** (plasma levels of isoflavones at baseline = daidzein\_EP\_nmol + genistein\_EP\_nmol + glycitein\_EP\_nmol + equol\_EP\_nmol)

**phytoestrogens\_EP\_nmol** (plasma levels of total phytoestrogens at baseline = enterolactone\_EP\_nmol + enterodiol\_EP\_nmol + lariciresinol\_EP\_nmol + seco\_EP\_nmol + daidzein\_EP\_nmol + genistein\_EP\_nmol + glycitein\_EP\_nmol + equol\_EP\_nmol)

phytoestrogens\_BL\_nmol (plasma levels of total phytoestrogens at endpoint =
enterolactone\_BL\_nmol + enterodiol\_BL\_nmol + lariciresinol\_BL\_nmol + seco\_BL\_nmol +
daidzein\_BL\_nmol + genistein\_BL\_nmol + glycitein\_BL\_nmol + equol\_BL\_nmol)

lignans\_diff\_nmol = lignans\_EP\_nmol - lignans\_BL\_nmol

isoflav\_diff\_nmol= isoflavones\_EP\_nmol - isoflavones\_BL\_nmol

phyto\_diff\_nmol= phytoestrogens\_EP\_nmol - phytoestrogens\_BL\_nmol

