### PLANS FOR STATISTICAL ANALYZES

### VARIABLES TO ANALYZE

Created variables (for more details see attached variable list):

BMI (kg/m^2): BMI\_stata = Weight\_inclusion / ((Lenght\_inclusion/100) \* (Lenght\_inclusion/100) BMI\_group = 1= under weight (BMI <18.5); 2= normal weight (BMI 18.5-24.9); 3= Overweight (BMI 25-29.9); 4= Obese class (BMI 30-34.9) 1; 5= Obese class ≥2 (BMI ≥35)

Weight change (kg): Weight\_diff = Weight\_endpoint - Weight\_inclusion

Analysis plan: PRODICA, [name]	Version 2
---------------------------------------	-----------

Compliance (1= compliance >80; 0= compliance <80 %): Compliance 24 recall (based on reported intake of phytoestrogens at the 24-h dietary recall) Compliance intervention 24 r (based on eaten interventions foods reported from at the 24-h dietary recall) Compliance intervention (based on eaten interventions foods reported from at the end of the intervention) Intake of isoflavones (µg): Isoflavones BL = Genistein N56 BL + Daidzein N57 BL + Formononetin N59 BL + Biochanin N60 BL + Equol N75 BL Isoflavones EP = GenisteinN56 EP + Daidzein N57 EP + Formononetin N59 EP + Biochanin N60 EP + Equol N75 EP. Intake of lignans (µg): Lignans BL = SECOtot N61 BL + Matairesinol N62 BL Lariciresinol N71 BL + Pinoresinol N72 BL + Syringaresinol N73 BL + Medioresinol N74 BL + Enterodiol N76 BL + Enterolactone N77 BL Lignans EP=SECOtot N61 EP + Matairesinol N62 EP + Lariciresinol N71 EP + Pinoresinol N72 EP + Syringaresinol N73 EP + Medioresinol N74 EP + Enterodiol N76 EP + Enterolactone N77 EP Intake of phytoestrogens (ug): Phytoestogens BL = (Isoflavones BL + Lignans BL + Coumestrol N58 BL) Phytoestogens EP =(Isoflavones EP + Lignans EP + Coursetrol N58 EP) Level of physical activity: Physical activity BL group = low, moderate or high 1 = Low physical activity (101, 102, 103 or 201 points) 2 = Moderate physical activity (104, 202, 203, 301 or 302 points) 3 = High physical activity (204, 303, 304, 401, 402, 403 or 404 points) Intake of fatty fish: Fat fish group BL:  $0 \le 1$  times/month; 1 = 1-3 times/month;  $2 \ge 1$  times/week Fat fish group EP: 0 = <1 times/month; 1 = 1-3 times/month; 2 = >1 times/week Fat fish diff: Fat fish month EP - Fat fish month BL

Use of antibiotics:

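### The per-protocol rule uses 160 mg as both the diet-arm floor and the control-arm ceiling, so control men who added phytoestrogen-rich foods up to almost 80% of the target can stay in as compliant

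*SAP*

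**What the plan says.** Under Additional analysis, the SAP plans an intention-to-treat analysis of everyone and a per-protocol analysis of participants with at least 80% compliance. In the diet arm, compliance means at least 80 "percent of the recommended intake of 200 mg of phytoestrogens, which is equal to" 160 mg or more. For the other arm: "In the control group, intakes below 160 mg of phytoestrogens will be considered compliant". No lower control ceiling, buffer zone or alternative cut-off is given.

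Four other sections bear on this:

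- HYPOTHESIS sets the comparator. The diet is "compared to an absence of the addition of phytoestrogen-rich foods during the same period".
- Definition of exposure fixes the coding by arm: "the participants in the control group are defined as not exposed", whatever they eat.
- STUDY DESIGN says of both arms: "Participants are instructed to avoid supplements but no other dietary restrictions are given". It schedules one 24-hour recall, partly "to estimate the intake of phytoestrogens in the control group".
- VARIABLES TO ANALYZE codes "Compliance (1= compliance >80; 0= compliance <80" per cent, for three different compliance variables. It also defines FFQ phytoestrogen intake at baseline (Phytoestogens_BL) and endpoint (Phytoestogens_EP).

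**The concern.** A per-protocol analysis is meant to show the effect among men who kept to their allocated arm. For the diet arm the rule does this: it asks for most of the target intake. For the control arm it only takes the complement of the diet-arm limit. It asks whether a control ate as much as a compliant diet-arm man, not whether he stayed with the comparator.

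A control who took up soy or flaxseed products after enrolment and reached 150 mg has departed from the stated comparator. He is still compliant under the rule and is analysed as unexposed. If phytoestrogens affect proliferation, men like him pull the control mean towards the diet-arm mean. A small or null per-protocol difference would then be harder to read, because part of it could reflect controls who took up the diet.

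**Working it through.** **Reproducing the SAP's figure.** 0.80 x 200 mg = 160 mg, as stated.

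**What the rule does at the boundary.** 159 / 200 = 79.5% of target. At 159 mg:

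| Arm | Rule | Status at 159 mg |
|---|---|---|
| Diet | 160 mg or more | not compliant, dropped |
| Control | below 160 mg | compliant, kept, coded unexposed |

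With a control ceiling C, the guaranteed gap between compliant men in opposite arms is 160 - C. At C = 160 it is effectively 0 mg. For illustration, C = 100 gives 60 mg and C = 40 gives 120 mg. This gap describes the worst-placed pair of men; it does not measure bias in the mean.

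**Possible dilution of the mean contrast.** The SAP gives no control intake distribution, so these inputs are assumptions: linear dose-response, compliant diet-arm men at 200 mg, a share q of controls raised to a mean of 100 mg, the rest at 5 mg.

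Contrast = 200 - [(1 - q) x 5 + q x 100]

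| q | Control mean (mg) | Contrast (mg) | Share of 195 mg retained |
|---|---|---|---|
| 0 | 5 | 195 | 100% |
| 0.10 | 4.5 + 10 = 14.5 | 185.5 | 95% |
| 0.20 | 4 + 20 = 24 | 176 | 90% |
| 0.30 | 3.5 + 30 = 33.5 | 166.5 | 85% |

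**A wider range.** Put a share f of controls at m mg and the rest at 0, so the share retained is 1 - f x m / 200. The power column further assumes 100 men per arm and 80% power at full contrast, two-sided 5%. The SAP states no power or effect size.

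| f | m = 80 to 159 mg: retained | Power |
|---|---|---|
| 0 | 100% | 80% |
| 0.05 | 98% to 96% | 78% to 77% |
| 0.10 | 96% to 92% | 77% to 73% |
| 0.25 | 90% to 80% | 71% to 61% |
| 0.50 | 80% to 60% | 61% to 39% |

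**Which controls matter.** Take two controls, both at 100 mg at endpoint. One started at 5 mg and so added 95 mg; the other has always eaten 100 mg and added nothing. Only the first departs from the hypothesis. The present rule keeps both, a 40 mg ceiling would drop both, and a rule on change from baseline tells them apart.

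**The case against.** The strongest reply is that the comparator is absence of the *addition*, not absence of phytoestrogens. Controls had no intake limit, so a habitual consumer at 60 or 100 mg has broken no instruction. This stands. A reader might infer that any sizeable control intake is contamination, or that controls should be capped at 40 mg as the mirror image of the 80% rule. The SAP supports neither. The 40 mg figure has no source in it, and a fixed low ceiling would remove adherent men for their usual diet. That is further post-randomisation selection in one arm, on a variable tied to other dietary factors which the SAP lists as possible confounders. If the single 24-hour recall defined the set, one unusual day could exclude a man.

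Three further replies have weight:

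- The dilution is conditional, and the first illustration retains 85-95% of the contrast.
- The rule removes controls at 160 mg or more, so it leaves the control arm no more diluted than the intention-to-treat analysis does.
- Crude models C2-C5 and their counterparts relate outcomes to actual endpoint intake regardless of arm.

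The last point does not repair the per-protocol set, which remains a comparison by arm. Nor does the first reply cover the man who did add the foods: the rule keeps him too, against the SAP's own comparator.

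**Conclusion.** The point holds in a limited form. The control-arm rule does not test adherence to the comparator in the hypothesis, and it guarantees no separation between the arms. It *can* therefore dilute the per-protocol contrast towards no effect if some controls added phytoestrogen-rich foods and intake has an effect.

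A reader might go further and conclude that the contrast *is* diluted, or that a null per-protocol result would be uninterpretable. The documents do not support either. The size depends on an intake distribution that the SAP does not give. It is zero if no control has substantial intake, and about 5-15% of the contrast under the 10-30% scenarios. Larger losses need a quarter to a half of controls at 80 mg or more. Harder to interpret is a fair description.

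The defect is confined to the per-protocol analysis, one of the additional analyses; the all-participants comparison is unaffected. It should still be corrected, because the SAP already has the variables needed.

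**What to change.** Before the data are seen:

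1. Define control-arm adherence for the per-protocol set as no material increase from the man's own baseline, using Phytoestogens_EP minus Phytoestogens_BL, and write down the margin in advance. Both variables are in µg while the present rule is in mg, so state the unit.
2. Add one sensitivity analysis with a lower absolute ceiling, for example 20% of target (0.20 x 200 = 40 mg). This is an illustrative analysis cut-off only, not a limit on anyone's diet.
3. Name the variable that defines compliance in each arm. Three are listed, and the two based on intervention foods have no evident meaning for controls. Align the coding at exactly 80%, which the variable list leaves unassigned and the per-protocol text includes.
4. Leave the all-participants comparison unchanged.

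The cost is a few sentences and one extra analysis. Some control men leave the per-protocol set, which adds some post-randomisation selection, and the change score carries FFQ measurement error from two occasions. Report the numbers excluded, by arm, under each definition.

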#### NUMBER OF SUBJECTS

The person time studied will be 203 person moments. Interim analyzes will be made when there is data to analyze 100 person moments.

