### Definition of effect modifying factor

The individual genotype (alleles TT, TC or CC) of the estrogen-beta-gene (ERB) are identified in the blood sample at baseline.

**cat\_genotype** (created from variable Genotype, 0=TT, 1= TT/CC)

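### The intake-plasma regression is fitted only by arm and genotype, in a sub-group of unstated size, with no arm-adjusted overall slope and no test that the slopes differ

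*SAP*

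**What the plan says.** The SAP section on the definition of exposure limits the plasma measurements: they are taken "in plasma for a sub-group of participants". It gives no size or selection rule for this sub-group.

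The section "Additional analysis" has a block with the stated purpose "Investigate the effects of the intervention diet on plasma concentrations of phytoestrogens". The block contains two analyses:

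- Cohen's kappa compares intake tertiles with plasma tertiles. It is not described as stratified.
- Linear regressions have estimated intake as explanatory variable and plasma concentration as outcome. Of these the SAP says: "The regression model will be stratified according to the intervention- and control groups and genotype".

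The text does not say whether arm and genotype are crossed (four fits) or taken one at a time (two fits plus two). It neither promises nor excludes an overall fit. It names no method for combining the stratum slopes or comparing them. By contrast, the section on stratification by ERß alleles pairs stratification of the outcome models with a product term.

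**The concern.** Reported intake is the exposure in crude models C2 to C5 and their counterparts for PSA and hormones. The kappa and this regression are the SAP's only comparisons of reported intake with an internal measure. If the kappa is computed across both arms, it may largely reflect allocation. That leaves the regression as the comparison that can look within arms.

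Splitting a reduced data set into small fits has two consequences. A real relation may be missed in each fit. A relation that appears in one stratum and not in another may be read as a difference when it is chance. Keeping the arms apart is sound, because allocation shifts both intake and plasma level. A joint model with an arm term does the same while using all the data.

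**Working it through.** **Inputs.** The SAP gives no alpha, power, correlation, sub-group size, allocation ratio or genotype frequencies for this regression, so there is no figure of its own to reproduce. From the SAP:

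- There are two arms (study design).
- Genotype has two levels (definition of the effect modifying factor, printed as "created from variable Genotype, 0=TT, 1= TT/CC"). Only the number of levels is used here.
- The overall size is given as 203 person moments (number of subjects). This is not the plasma sub-group and serves only as a ceiling.

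Assumed: two-sided 0.05, 1:1 arms, a 40/60 genotype split, sub-group size N of 40 to 203, and within-stratum correlation r of 0.2 to 0.7.

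**Formula.** Power of a slope (correlation) test by Fisher z:

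power ≈ Φ(atanh(r)·√(n−3) − 1.96) + Φ(−atanh(r)·√(n−3) − 1.96)

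**Reading 1: four crossed cells, common slope.** Take N = 60 and r = 0.3, so atanh(0.3) = 0.3095. The second term adds at most about 0.002.

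- All 60 men: 0.3095 × √57 = 2.337, and Φ(2.337 − 1.96) ≈ 65%. Allowing for the arm and genotype terms replaces √57 by √55, which gives 2.295 and about 63%.
- Small cell, 60 × 0.5 × 0.4 = 12 men: 0.3095 × √9 = 0.929, about 15%.
- Large cell, 60 × 0.5 × 0.6 = 18 men: 0.3095 × √15 = 1.199, about 22%.

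The same formula over a range, with the first column on all N men:

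| N | r | All sub-group data | Single crossed cell |
|---|---|---|---|
| 40 | 0.5 | 92% | 23-38% |
| 60 | 0.3 | 65% | 15-22% |
| 60 | 0.5 | 99% | 38-57% |
| 60 | 0.7 | 100% | 74-92% |
| 100 | 0.3 | 86% | 25-36% |
| 100 | 0.5 | 100% | 62-81% |
| 203 | 0.3 | 99% | 48-65% |

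The loss therefore runs from large to modest, depending on inputs the SAP does not give.

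**Reading 2: one factor at a time.**

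- By arm, the loss is milder. With 30 men per arm, power is about 36% at r = 0.3 and 81% at r = 0.5.
- By genotype, each fit mixes both arms and no arm term is stated. Let the within-arm correlation be zero and the arms lie D_x and D_y within-arm SDs apart on intake and plasma. The mixed correlation is (D_x·D_y/4) / √[(1 + D_x²/4)(1 + D_y²/4)]. With D_x = D_y = 2 this is 1/√(2 × 2) = 0.50. A correlation of 0.50 is detected with about 71% probability in 24 men and 88% in 36. A genotype fit would then often show a relation that is only allocation.

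**Chance differences between strata.** Suppose both arms have the same slope, r = 0.3, with 30 men each and power p = 0.36. The chance that exactly one arm is significant is 2p(1−p) = 2 × 0.36 × 0.64 = 46%. A simulation of 3000 data sets also gave 46%.

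**The case against.** A reader might infer that stratifying costs the analysis most of its power. The SAP does not support that as a general statement. Sub-group size, genotype split, correlation and crossing rule are all missing, and at N = 100, r = 0.5 or N = 60, r = 0.7 each cell keeps 62-92%. This objection stands.

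Second, the single model's advantage assumes a common slope, while stratifying makes sense precisely when slopes may differ. In a simulation of 1000 data sets with a relation in the intervention arm only (r = 0.4, control 0), the ranking against arm-level fits reversed:

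| N | Intervention-arm fit | Common slope | Intake × arm term |
|---|---|---|---|
| 60 | 62% | 35% | 32% |
| 40 | 43% | 25% | 22% |

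This also stands, and it is why the stratum fits should stay. It applies to fits by arm. Four crossed cells gain little even then: at r = 0.4, cells of 12 and 18 men have 25% and 37%.

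Third, elsewhere in the SAP stratified analyses come on top of overall ones, so an overall fit may be intended. That is possible, but none is stated, and an unstated overall fit without an arm term would have the allocation problem of Reading 2. Combining the four stratum estimates would recover most of the precision (97% against 99% at N = 60, r = 0.5), but no combination is planned.

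Fourth, the block's stated purpose is the effect of the diet on plasma levels. No success criterion rests on this regression, and the randomised comparison C1 does not use reported intake. This limits the point's weight but does not remove it.

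**Conclusion.** The point holds in a limited form. The plan names no arm-adjusted overall slope and no comparison of slopes for a regression confined to a sub-group of unstated size, and both readings of the stratification leave a weakness. Under crossing with a common slope, power per fit can be far below that of one joint model: 15-22% against about 65% at the assumed N = 60 and r = 0.3, with a smaller gap at higher r or N. Under one factor at a time, the genotype fits can show a relation produced by allocation alone. The documents do not show that the stratum fits are wrong, nor that a common slope is always better. For an additional, descriptive analysis the severity is minor.

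**What to change.** In the SAP's additional analyses:

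- State the size of the plasma sub-group and whether arm and genotype are crossed.
- Keep the planned stratum-specific slopes.
- Alongside them, fit one linear regression of plasma concentration on intake in the whole sub-group, with Group_intervention and cat_genotype as terms.
- Add intake × arm and intake × genotype product terms, and report them with confidence intervals before claiming that any strata differ.

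The cost is a few lines of wording and no new data. There are two downsides to state in the text. The combined slope assumes a common relation, and the product-term tests have limited power, so a non-significant product term should not be read as equal slopes.
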